### 4.2 Secondary Hypotheses

The secondary hypotheses are:

1. Compared to baseline, treatment with IFN- $\gamma$ 1b will result in:
  - a. Decreased tibial volumetric bone mineral density (**vBMD**) and estimated bone strength measured by peripheral quantitative computed tomography (**pQCT**);
  - b. Decreased total body and lumbar spine areal BMD (**aBMD**) by dual-energy x-ray absorptiometry (**DXA**);
  - c. Increased levels of markers of bone remodeling (see Table 1);
  - d. Increased osteoclast activity by *in vitro* testing;
  - e. Increased white blood cell (**WBC**) and platelet counts in patients that have lower than expected blood counts at baseline.
  - f. Increased height standard deviation score (**SDS**) for participants <18 years with open growth plates;
  - g. Decreased inflammation measured by erythrocyte sedimentation rate (**ESR**);

[figure not shown]
- h. Decreased pain score (based on prior 4 weeks);
  - i. Increased physical function score (based on prior 4 weeks); and
2. Compared to the 12 months prior to study entry (based on medical record review or subject recollection), treatment with IFN- $\gamma$ 1b over 12 months will result in:
  - a. Decreased number of hospitalizations for infection;
  - b. Decreased number of days treated with antibiotics;
  - c. Beneficial change in WBC and platelet counts in patients who have lower than expected blood counts at baseline;
  - d. Beneficial change in ESR;
  - e. Increased height SDS for participants  $<18$  years with open growth plates; and
3. Patients will not develop neutralizing antibodies.

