## 5.3 Evaluations and study timeline

Table 1. Evaluations and study timeline

	Screening a	Baseline	# of months from 1 st IFN- $\gamma$ 1b treatment ( $\pm$ 1 week)		
			3	6	12
General					
• Medical history	X	X	X	X	X
• Physical exam		X	X	X	X
• Genotype b		X			
• Anthropometric measurements	X	X f	X	X	X
• RNA and DNA assays		X	X	X	X
Safety Measuresc					
• Basic metabolic panel (BMP)	X	X	X	X	X
• Liver function tests (LFT)	X	X	X	X	X
• Urine pregnancy test (UPT) e	X	X	X	X	X
• Urinalysis (UA)	X	X	X	X	X
• ECHO with interpretation	X				
• EKG with interpretation	X				

• Anti-drug antibodies (ADA) g		X	X	X	X
Bone Biomarker Testingd					
• Formation Testing (bone specific alkaline phosphatase [BAP], type 1 procollagen [P1NP])	-	X	X	X	X
• Resorption testing (C-telopeptide [CTX], Tartrate resistant acid phosphatase type5b [TRAP5b])	-	X	X	X	X
• RANKL, OPG, CK-BB	-	X	X	X	X
Endocrine Assessment					
• Total 25-OH Vitamin D (25OHD) h	-	X	X	X	X
• Serum ionized calcium	-	X	X	X	X
• Urine calcium: creatinine	-	X	X	X	X
• Intact parathyroid hormone (iPTH)	-	X	X	X	X
Inflammatory/Immunology					
• CBC with differential and platelets	-	X f	X	X	X
• Erythrocyte sedimentation rate (ESR)	-	X f	X	X	X
• Immunologic phenotyping (CD3, 4, 8, 14, 15, 16, 19, 34, 56)	-	X	X	X	X
Neuropsychological testing					
• Pain assessment	-	X	X	X	X
• Quality of life survey	-	X	X	X	X
Orthopedic assessment					
• Dual energy X-ray absorptiometry (DXA) lumbar spine, total body, total hip and femoral neck (adults $\geq 18$ yrs only)	-	X	-	-	X
• Peripheral Quantitative CT (pQCT) left tibia	-	X	-	X	X
In vitro osteoclast function assays – [name] Lab					
• Gene expression – osteoclast marker genes	-	X	X	X	X
• Osteoclast activity – ability to release calcium phos from coated plate	-	X	X	X	X
Infectious outcomes					
• Number of hospitalizations in prior 3 months	-	X f	X	X	X
• Number of days treated with antibiotics in last 3 months	-	X f	X	X	X
• Type of infectious organism	-	X f	X	X	X
RANKL=Receptor activator of nuclear factor kappa-B ligand; OPG=osteoprotegerin; CK-BB=creatinine kinase isoenzyme BB.					
a Screening visit evaluations will count for baseline evaluations where applicable. Screening visit will be within 3 months of baseline visit					

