## 6.3 Clinical Procedures

### 6.3.1 Medical History

A study physician and/or study coordinator will review the following with the subject/parent or legal guardian at the screening baseline visit:

- Current and past 1 year prescription medications and doses,
- current and past medical history,
- review of systems,
- family history,
- number of hospitalizations over the last 12 months, and

- number of days treated with antibiotics over the last 12 months.

For patients <18 years of age, height data will be collected from 6 and/or 12 months prior to the baseline visit.

Changes in the medical history and a complete review of systems will be reviewed at each subsequent visit.

If a subject is unable to return to the clinical site for the Month 3 visit they will be contacted via telephone to discuss any changes in health since their last study visit and then withdrawn from the study. Three attempts will be made to contact the subject by phone before terminating the patient on the study.

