### **6.3.5.4 Infectious Outcomes**

The frequency of infectious outcomes will be quantified by asking participants for the number of hospitalizations in the last 3 months and the number of days treated with antibiotics over the last 3 months (IV and PO will be counted separately). The type of infectious organism will be documented as well.

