#### **6.5 Study Protocol Compliance / Treatment Adherence**

Adherence to treatment will be evaluated by querying subjects every month either at scheduled study visits or by phone.

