#### **6.7 Protocol Amendments After Study Initiation**

Should changes in the study plan or protocol become necessary in the course of the study, those specific changes will be discussed and agreed upon by the Investigators and appropriate IRB approval obtained before the changes are implemented. All changes must be documented as protocol amendments.

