#### **6.8 Subject Withdrawal**

Subjects will be encouraged to complete the study; however, they may voluntarily withdraw at any time. If a subject is withdrawn prior to study completion, attempts will be made to schedule and conduct an Early Termination visit for medical assessment. If a subject cannot be contacted after 5 telephone calls and 3 letters, they will be considered lost to follow-up.

Subjects who discontinue study medication (e.g., due to non-compliance, side effects, etc.) will be asked to remain in the study for follow-up per the study schedule to preserve the ability to perform a

safety analysis. If a subject or their legal guardian (as applicable) withdraws consent to participate in the study, attempts will be made to obtain permission to record survival and adverse event (malignancy, hospitalization for infection) data at the 12-month study point.

As long as the link between the sample ID code and the subject name is maintained by the clinical study site, it will be possible for subjects to ask that their samples be withdrawn. However, we anticipate this link will be destroyed at some point in the future, after which withdrawal of samples will not be possible. In addition, once DNA samples have been provided to collaborators, we cannot guarantee that all samples will be able to be tracked down.

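### The scheduled infection items miss treated months 6 to 9, so they do not cover the 12-against-12-month comparison in hypotheses 2a and 2b

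*Combined protocol and SAP*

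**What the plan says.** - **Hypotheses.** Section 4.2, item 2, sets the reference period: "Compared to the 12 months prior to study entry (based on medical record review or subject recollection"). Treatment over 12 months is expected to reduce hospitalizations for infection (2a) and antibiotic days (2b).
- **Pre-entry history.** Section 6.3.1 takes a 12-month history at screening/baseline, including the "number of days treated with antibiotics over the last 12 months" and a count of hospitalizations over the same period. That count is not limited to infection.
- **Items during treatment.** Section 6.3.5.4 asks for the "number of hospitalizations in the last 3 months and the number of days treated with antibiotics over the last 3 months", with IV and oral antibiotics counted separately.
- **Schedule.** The row in Table 1 reads "Number of hospitalizations in prior 3 months" and is marked at baseline and months 3, 6 and 12. Appendix B has the same label and the same marks, and its month 9 infection cells are blank. Month 9 carries safety laboratory tests, which section 6.3.2 allows at a local laboratory; Appendix B adds a pregnancy test.
- **Analysis.** Section 7.2.2 tests change from baseline to 12 months for hematologic function, immune function and bone mineral density. It does not name the infection outcomes and does not mention unequal observation time.

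**The concern.** A 3-month look-back covers the whole treated year only if it is asked every 3 months, and the month 9 questioning is absent. Followed to the letter, the collection rule gives 9 treated months to set against 12 pre-entry months. The analysis section says nothing about adjusting for the difference, and the shortfall favours the drug.

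Two definitional problems sit alongside this:

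- Hypothesis 2a concerns admissions for infection, but the hospitalization items in sections 6.3.1 and 6.3.5.4, Table 1 and Appendix B do not say so. In 6.3.5.4 and the tables the infectious-outcomes heading may imply it. In 6.3.1 nothing does.
- The baseline row in both tables is labelled 3 months, while 4.2 and 6.3.1 use 12.

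The stakes are moderate. Section 2.3 intends to use encouraging efficacy data to raise clinicians' awareness of the treatment, and section 7.2.1 says the pilot is to inform a definitive trial.

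**Working it through.** The plan states no coverage figure, so there is none to reproduce.

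**Inputs**
- Look-back of 3 months (6.3.5.4, Table 1, Appendix B).
- Post-baseline infection items at months 3, 6 and 12, with visits within 1 week of target (Table 1, Appendix B).
- Comparison of 12 treated months with 12 pre-entry months (4.2).
- Assumption for the day-level check: a 91-day look-back and visits at days 91, 182 and 365.

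**Coverage in months**
- Month 3 item: months 0 to 3. Month 6 item: months 3 to 6. Month 12 item: months 9 to 12.
- Union = 3 + 3 + 3 = 9 months; 9/12 = 75%. Months 6 to 9 fall in no item.

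**Can the visit window close the gap?**
- Gap = month 12 visit day − 91 − month 6 visit day.
- Nominal: 365 − 91 − 182 = 92 days.
- Smallest: 358 − 91 − 189 = 78 days.
- Largest: 372 − 91 − 175 = 106 days.
- Share of treated days covered: nominal 273/365 = 74.8%; lowest 259/372 = 69.6%; highest 273/358 = 76.3%.

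These ranges hold for visits kept within 1 week of target. They are not absolute bounds, because section 5.4.8 treats the month 3 visit as missed only after 120 days.

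**Effect on the comparison**

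Let the monthly rate be r, unchanged by treatment.
- Unscaled totals: 9r / 12r = 0.75, an apparent fall of 25%.
- Per month observed: (9r/9) / (12r/12) = 1.00, no apparent change.
- With months 6 to 9 collected: 12r / 12r = 1.00.

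No false-positive rate is given, because the documents state no infection rates from which to calculate one.

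**Why scaling alone is second best**

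Under section 6.3.6 the first 9 weeks (63 days) are titration. The scheduled items capture all of that time but omit 92 later days. Titration is then 63/273 = 23% of captured time, against 63/365 = 17% of treated time. A rate based on 9 months assumes that the missing quarter resembles the rest.

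**The case against.** **Other records may reach months 6 to 9.** This is the strongest reply. Section 6.5 provides monthly contact: "Adherence to treatment will be evaluated by querying subjects every month either at scheduled study visits or by phone". Section 8.2 requires adverse event questioning at every contact, 8.1 counts intercurrent illness as an adverse event, and most admissions would be reported as serious. Section 6.3.1 adds that "Changes in the medical history and a complete review of systems will be reviewed at each subsequent visit", and its list of history items includes antibiotic days, so the month 12 review could be read as updating them since month 6. Section 6.8, for subjects who withdraw consent, seeks "permission to record survival and adverse event (malignancy, hospitalization for infection) data at the 12-month study point".

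Much of this stands for 2a. A reader might infer that infections in months 6 to 9 are lost altogether, or that 2b cannot be tested over 12 months; the documents do not support going that far. What remains is that no passage links these records to 2a or 2b, and none expressly asks for an antibiotic-day count, IV and oral separately, over those months. An adverse event entry for an infection is not such a count.

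**Section 4.2 already fixes the windows.** This is correct. A reader might infer that the analyst is free to pair any treated window with any baseline window, with widely different results. Section 4.2 prescribes 12 months against 12, so other pairings would depart from the hypothesis. Reading 7.2.2 literally with Table 1, the month 12 item against the 3-month baseline item is neutral (3/3 = 1), but it uses a quarter of treated time and does not test hypothesis 2. The live problem is a 9-month total used where 12 months are specified.

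**Immune function in 7.2.2 may be meant to include infections.** That is possible, but the section would still give no scaling for observation time.

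**The baseline labels need not conflict.** Both a 3-month and a 12-month count could be collected. The labels need reconciling; they are not a proven contradiction.

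**Conclusion.** The gap is real and should be fixed. The scheduled infection items cover 9 of 12 treated months (75%; about 70% to 76% under the stated visit-window assumptions) and omit months 6 to 9. The point is firm for antibiotic days (2b) and weaker for hospitalizations (2a), where safety reporting should capture many events.

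The apparent 25% fall is conditional. It assumes a constant rate, no drug effect, collection exactly as scheduled, and an unscaled 9-month total set against the 12-month history. The plan does not say that the analysis will be done that way, and it does not rule it out.

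These are secondary outcomes in an uncontrolled 10-subject pilot, and the primary endpoint of feasibility and tolerability is unaffected. Regression to the mean, in subjects who enter because of a serious infection in the prior year (5.4.5, item 6), limits interpretation separately and would remain after the fix.

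**What to change.** 1. **Close the gap.** In 6.3.5.4, Table 1 and Appendix B, change the post-baseline look-back to the time since the previous visit. Alternatively, keep 3 months and add the items at the existing month 9 contact. Either gives 12 of 12 months.
2. **Use one definition before and during treatment.** In 6.3.1, 6.3.5.4 and both tables, record hospitalizations for infection and antibiotic days, IV and oral separately. Label the baseline row as the prior 12 months, to match 4.2 and 6.3.1. The definition must change in 6.3.1 too. Restricting only the treated-period item to infection would set infection admissions against all pre-entry admissions, which would favour the drug.
3. **State the analysis.** In 7.2.2, name both infection endpoints and compare rates per subject-month observed with the 12-month history. This also handles any subject whose months 6 to 9 were not recorded.

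With item 1 in place, 2a does not need to be filled in from serious adverse event reports. Doing so would mix sources, and the hospitalization definition in 8.1 leaves out some admissions.

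**Cost.** A short amendment to three sections, two tables and the case report form, with "appropriate IRB approval obtained before the changes are implemented" (section 6.7). The added burden is either a 6-month recall at month 12, which may be less accurate, or about three items (infection admissions, IV days, oral days) at an existing contact. No visit is added.

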### **6.3.5.5 In vitro osteoclast function assays**

Osteoclasts will be isolated from whole blood by Ficoll gradient and CD14+ selection. The CD14+ cells will be cultured in macrophage colony stimulating factor (M-CSF) and

RANKL until multinuclear, TRAP positive cells are present in the culture. Assays will be performed to determine the direct and indirect effects of IFN $\gamma$ -1b as follows:

- normal osteoclasts
- normal osteoclasts + IFN- $\gamma$ 1b (0.25 ng/ml, 0.5 ng/ml, and 1.0 ng/ml),
- diseased osteoclasts (baseline)
- diseased osteoclasts (baseline) + IFN- $\gamma$ 1b (0.25 ng/ml, 0.5 ng/ml, and 1.0 ng/ml)
- diseased osteoclasts (month 6)
- diseased osteoclasts (month 6) + IFN- $\gamma$ 1b (0.25 ng/ml, 0.5 ng/ml, and 1.0 ng/ml)
- normal osteoclasts + 10% serum from treated patients
- diseased osteoclasts (baseline) + 10% serum from treated patients
- diseased osteoclasts (month 6) + 10% serum from treated patients

Outcome measures will be as follows:

For phenotypic analysis, gene expression (osteoclast marker genes such as but not limited to *c-fos*, *Nfatc1*, *DC-STAMP*, *cathepsin K*) will be measured by real time RT-PCR. Osteoclast cultures will be stained for TRAP, photographed and osteoclast size and number will be measured. Osteoclast cultures will also be plated on calcium phosphate coated dishes and activity of the osteoclasts (ability to release calcium phosphate from coated plate) will be evaluated. Calcium phosphate dishes will be treated, photographed and percent area of the well absorbed, number of resorption pits and average size of the pit will be measured. All of the data collected will be used to determine if changes in differentiation and/or activity are occurring in the osteoclasts in response to treatment.

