## 6.2.2 Research Specimen Handling and Storage (See Manual of Operations for instructions for non-LA BioMed sites)

### Samples for Bone Biomarkers and Storage

Plasma. Collect blood in 3 purple-top (ethylenediaminetetraacetic acid [EDTA]) tubes (4 mL each). After collection, thoroughly mix the tube by gentle inversion 8 times. Label the tube with the Subject's Study ID number, study visit, date of visit, and "plasma". **Do not write the subject's name or any other identifying information on the blood tube.** Place the tube upright in a rack in the refrigerator (2 to 8°C) until processed and stored at -80°C.

If need to transport to the lab for processing, wrap the tube in a paper towel and place it in a plastic bag with an absorbent pad. Place the plastic bag containing the tube in a Styrofoam mailer with a frozen gel pack or on ice. The gel pack will ensure refrigerator temperature (2 to 8°C) during transport to the laboratory.

2 tubes: Centrifuge for 15 minutes at 4000 x g within 30 minutes of collection. Aliquot 0.5 ml into each 2 ml cryovial (8 cryovials) and store samples at -80°C.

1 tube: Invert 8-10 times immediately after drawing. Keep tube cooled on ice, or with a cold pack, or in a 4C refrigerator. Transport to Translational Genomics & Population Sciences laboratory on ice for processing and storage of buffy coat.

Serum. Collect blood in 2 red-top (serum separator tube [SST]) tubes (5 mL each). After collection, allow blood to clot for 30 minutes. Label the tube with the Subject's Study ID number, study visit, date of visit, and "serum". **Do not write the subject's name or any other identifying information on the blood tube.** Place the tube upright in a rack in the refrigerator (2 to 8°C) until processed and stored at -80°C.

If need to transport to the lab for processing, wrap the tube in a paper towel and place it in a plastic bag with an absorbent pad. Place the plastic bag containing the tube in a Styrofoam mailer with a frozen gel pack or on ice. The gel pack will ensure refrigerator temperature (2 to 8°C) during transport to the laboratory.

Centrifuge for 15 minutes at 4000 x g within 30 minutes of collection. Aliquot 0.5 ml into each 2 ml cryovial (10 cryovials) and store samples at -80°C.

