### **Whole Blood**

#### *Ex vivo assays:*

**Collect 1 purple-top (EDTA) tube (10 mL).** Label the tube with the Subject's Study ID number, study visit, date of visit, and "whole blood". **Do not write the subject's name or any other identifying information on the blood tube.** Send to [name] per instructions below for arrival at [name] lab within 36 hours of sample collection.

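### The osteoclast wells with treated-patient serum have no untreated-serum comparator, so a serum-mediated effect of interferon cannot be separated from the effect of adding patient serum

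*Combined protocol and SAP*

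**What the plan says.** Section 6.3.5.5 gives the purpose: "Assays will be performed to determine the direct and indirect effects of" the study drug. It then lists nine lines of conditions. Each of three cell sources (normal, patient at baseline, patient at month 6) appears alone, with interferon added at 0.25, 0.5 and 1.0 ng/ml, and with serum. The serum lines are "normal osteoclasts + 10% serum from treated patients", "diseased osteoclasts (baseline) + 10% serum from treated patients" and "diseased osteoclasts (month 6) + 10% serum from treated patients". The section closes by giving every condition the same use: "All of the data collected will be used to determine if changes in differentiation and/or activity are occurring" in response to treatment.

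The section does not say when the treated serum is drawn, whether it comes from the subject who gave the cells, or what the base culture medium contains. Table 2 lists only EDTA whole blood for the ex vivo assays. Section 6.2.2 wants that blood at the assay laboratory "within 36 hours of sample collection". Serum is collected separately under Section 6.2.2: "Aliquot 0.5 ml into each 2 ml cryovial (10 cryovials) and store samples at -80°C". Section 7.2.2 makes the in vitro endpoints descriptive.

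**The concern.** A serum-transfer experiment asks whether treatment changed something in the blood that acts on osteoclasts. To answer it, serum after treatment has to be compared with serum before treatment. Here it is compared with no patient serum at all.

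If the wells with treated serum resorb more, or less, than the plain wells, the difference could arise wholly from adding patient serum, with nothing contributed by interferon. Because the section uses all of the data to judge response to treatment, such a difference could be read as an indirect drug effect. What is at stake is the serum-mediated part of the mechanism, which a pilot of this kind might carry forward into the rationale for a larger trial.

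**Working it through.** The plan gives no figure to reproduce on this point. The check is whether the listed conditions allow the treatment effect on serum to be estimated.

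**Step 1. Conditions (Section 6.3.5.5).**

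| Cells | No addition | Added interferon | Treated-patient serum, 10% | Untreated serum, 10% |
|---|---|---|---|---|
| Normal | listed | 3 concentrations | listed | not listed |
| Patient, baseline | listed | 3 concentrations | listed | not listed |
| Patient, month 6 | listed | 3 concentrations | listed | not listed |

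The distinct conditions number 3 × (1 + 3 + 1) = 15. Tables 1 and 2, Section 6.2, Section 7.2.2 and Appendix B were read for an untreated-serum condition. None supplies one.

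**Step 2. What the available contrast estimates.** For one cell source, let μ be the mean with no addition, σ the effect of adding osteopetrosis-patient serum, and τ the further effect of that serum having been taken under treatment.

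- Plain well: μ
- Treated-serum well: μ + σ + τ
- Difference: σ + τ

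A difference D fits τ = 0 with σ = D as well as it fits σ = 0 with τ = D. Replication makes D more precise but does not divide it.

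**Step 3. The same result for the whole list.** Fit an additive model with an intercept (1), cell source (2), interferon concentration (3), serum added (1) and serum from a treated patient (1), which is 8 parameters. Over the 15 conditions the last two columns are identical, and the rank of the design matrix is 7. Neither serum term is estimable alone; only their sum is.

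**Step 4. With a control.** Adding one untreated-serum condition per cell source gives 15 + 3 = 18 conditions and rank 8 of 8. Both serum terms become estimable. Within a cell source:

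(μ + σ + τ) − (μ + σ) = τ

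**Step 5. Which control.** Split σ into a part from any human serum (h) and a part from the disease (d). Against healthy-donor serum the contrast is (h + d + τ) − h = d + τ, so disease stays mixed with treatment. Against the same donor's Baseline serum it is (h + d + τ) − (h + d) = τ. The donor's own Baseline serum is therefore the better control.

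**Step 6. Volume.** One 0.5 mL aliquot used at 10% makes 0.5 / 0.10 = 5 mL of medium. The documents give no well volume. Assuming 0.2 to 1.0 mL per well, that is 5 / 1.0 = 5 wells to 5 / 0.2 = 25 wells, before any medium change. Section 6.2.2 describes 10 × 0.5 = 5 mL of serum from the two biomarker-and-storage tubes, and CK-BB also needs serum. Feasibility is plausible but has to be confirmed.

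**The case against.** The best reply is that little rests on these wells. The trial is a 10-subject pilot with a feasibility and tolerability primary objective, and no dosing, safety or primary conclusion uses the assays. That stands, and it limits the weight of the point. A descriptive analysis does not cure the problem, though, because what is missing is the comparison, not a test of it.

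Several stronger readings are tempting, and the documents do not support them.

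- *That the direct/indirect aim as a whole fails.* The added-interferon conditions each have a matching no-addition condition. Month-6 against baseline cells also carries information on treatment in vivo. The section never labels the serum wells as the indirect test; that is a sensible inference, not a statement in the plan.
- *That a serum artefact would be reported as support for hypothesis 1d.* Section 4.2 words 1d as a change from baseline in osteoclast activity, which baseline and month-6 cells answer without the serum wells. Nothing says the serum wells will be used for 1d.
- *That the baseline-cell serum condition cannot use the subject's own treated serum.* The Table 2 column asks only about batching at the end of the study, and the 36-hour limit governs arrival at the laboratory. Neither rules out storing cells until treated serum exists. What can be said is that the source is not stated.
- *That RANKL, OPG and PTH are measured because they vary and would drive the serum effect.* The plan gives no such reason for measuring them.

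The base medium is also unspecified, and the Manual of Operations cited for specimen handling is not among the documents. If control wells already contain some other serum, the size of h changes, but disease and treatment remain mixed.

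**Conclusion.** The point holds for the serum contrast only. All 3 serum conditions, 3 of the 9 listed lines, lack an untreated-serum comparator, and the effect of treatment acting through serum cannot be identified from them at any sample size. Hypothesis 1d, the added-interferon conditions, the primary objective and the safety analyses are unaffected.

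The conclusion assumes that the list in Section 6.3.5.5 is complete and that the serum wells are meant to inform the indirect effect. It does not depend on an assumed effect size or variance. The change is worth making because it is cheap and because without it these wells cannot support a statement about interferon.

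**What to change.** For each serum condition that is kept, add paired wells with 10% serum from the Baseline visit of the person who gave the treated serum, on the same cells and the same plate. Define the serum-mediated effect in Section 6.3.5.5 as treated serum minus own Baseline serum, reported descriptively.

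In the same section, state:

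- the time point of the treated serum (Table 1 schedules the assays at months 3, 6 and 12, so more than one is possible);
- whether it is the subject's own or another subject's, in particular for the baseline-cell condition;
- the base medium.

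Record concomitant medication at each serum draw. Section 6.3.6 permits prednisone on injection days, and a Baseline control does not remove a difference in treated serum that comes from it.

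Use banked Baseline serum, after confirming that the volume is enough and that CK-BB and other planned uses are protected. It must travel frozen on dry ice. Section 6.2.3 sends whole blood from Harbor-UCLA at ambient temperature, so the serum cannot share that shipment. Stored samples are otherwise held at the sites until the end of the study, so early release needs to be written in.

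The cost is a few more wells and reagents (at most three further conditions, fewer if the baseline-cell condition is dropped), a frozen shipment and less banked Baseline serum. No extra draw, visit or staff is needed. If Baseline serum cannot be supplied, limit the conclusion to the effect of treated-patient serum versus none, and do not attribute it to interferon.
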